5.2.3 Safety laboratory parameters

For the sampling time points please see the [Flow Chart](#). All analyses will be performed locally and the respective reference ranges will be provided in the ISF. Patients do not have to be fasted for the blood sampling for the safety laboratory tests.

Clinically relevant abnormal findings as judged by the Investigator will be reported as adverse events (please refer to section [5.2.6](#)).

In case the criteria for hepatic injury are fulfilled, a number of additional measures will be performed (please see section [5.2.6.1.4](#) and the DILI Checklist provided in the ISF). The amount of blood taken from the patient concerned will be increased due to this additional sampling.

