5.2.3.3 Coagulation

Activated partial thromboplastin time (aPTT) or prothrombin time (PT) (expressed either in seconds or as percentage) will be tested.

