7.8.2 Laboratory data

The analysis of laboratory data will be descriptive in nature and will be based on BI standards (7). The same on-treatment period as considered for the analysis of adverse events will be applied for laboratory values. Patients having at least one post-baseline laboratory value will be displayed in the descriptive analyses. Patients with missing CTCAE grade at baseline or no baseline value but with post-baseline values will be displayed in a new category “missing CTCAE grade at baseline” for those laboratory parameters where CTCAE grading is applicable. Descriptive statistics, including change from baseline and frequency of patients with transitions relative to the reference range, will be provided. CTCAE grades for applicable laboratory parameters will be calculated according to CTCAE v5.0.

For Primary laboratory tests listed in Table [7.8.2: 1](#), the following outputs will be presented:

- Descriptive statistics, including changes from baseline
- Shift tables in terms of:
 - CTCAE grade, for laboratory tests with CTCAE grade defined;
 - Upper and lower reference limits, for laboratory tests without CTCAE grades;
 - Multiples of upper reference limit for customized shift tables of ALP, ALT, AST, total bilirubin and creatinine.
- Frequency of patients with potential clinically significant abnormalities.

For secondary laboratory tests listed in Table [7.8.2: 2](#), analyses will be limited to frequency of patients with potential clinically significant abnormalities.

For other laboratory tests, only listing of observed values will be presented.

Analyse of descriptive statistics should use normalized lab values. Analyses of frequencies of patients with potential clinical significance, analyses of shift, and liver function categories tables should use converted values.

Table 7.8.2: 1 Primary laboratory tests

Table 7.8.2: 2 Secondary laboratory tests

| Label | Lab test name | Direction of interest | Potential Clinical significance rule |
|-------|----------------------------|-----------------------|---|
| ALB | Albumin | Low | A ¹ |
| APTT | Activated Prothrombin Time | High | A ^{1,2} |
| CA | Calcium | Low, High | A ¹ |
| CL | Chloride | Low, High | Low: <80 mmol/L and <baseline High: >120 mmol/L and >baseline No CTCAE defined |
| EOS | Eosinophils | High | >1.0*10 ⁹ /L and > baseline No CTCAE defined |
| GGT | Gamma Glutamyl transferase | High | CTCAE Grade 2 or higher |

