| PHOS | Phosphate | Low, High | High: >1.7 mmol/L and >baseline Low: <0.7 mmol/L and <baseline No CTCAE defined |
| PROT | Serum Protein | High | >ULN and >baseline No CTCAE defined |
| PT | Prothrombin Time | High | >ULN and > baseline No CTCAE defined |
| URIC | Uric Acid | High | Females: >600 umol/L and >baseline Males: >650 umol/L and >baseline CTCAE based upon AE |

¹A= CTCAE grade 2 or greater with an increase of at least one CTCAE grade from baseline

²CTCAE grading will not consider symptoms presence of bleeding or use of anticoagulation.

Worst laboratory value and its CTCAE grade (highest CTCAE grade) over all courses will be calculated for each laboratory parameter.

The last laboratory value on treatment is the laboratory value of the last visit during the on-treatment period of each patient.

Laboratory values without CTCAE grading will be compared to their reference ranges and frequency tables will be provided for the number of patients within and outside the reference range at baseline, for the maximum value on treatment and for the last measurement on treatment.

Differential blood count:

Differential blood counts were to be measured in absolute values according to the CTP. In case a subject's differential blood count is reported in percentage, the following conversion will be applied:

$$\text{Differential } [10^9/\text{L}] = \text{Differential } [\%] * (\text{White blood cell count value} / 100)$$

The corresponding reference ranges of the converted differential blood values are not allowed to be converted like the individual laboratory measurements. The reference range is taken from the BI standard reference range definition.

Urine analysis based on dipstick:

To ensure medically rational and consistent BI internal handling of urine laboratory values assessed by dipstick only, no analyses based on CTCAE grades will be done for urine. For urine measurement based on dipsticks the indicated results will be converted as described in Table 7.8.2: 3 for the analysis and displayed in the urine analysis tables.

Table 7.8.2: 3 Conversion of urine measurements based on dipsticks

| Original dipstick measurement | Converted dipstick measurement |
|--|--------------------------------|
| “-” ; “NEG” ; “NEGATIVE” ; “NORMAL” | 0.0 |
| “0.5” ; “TRACES” ; “TRACE” ; “+/-” ; “+” ; “-/+” | 0.5 |
| “+” ; “1+”; “SMALL” | 1.0 |
| “++” ; “2+”; “MODERATE” | 2.0 |
| “+++” ; “3+”; “LARGE” | 3.0 |
| “++++” ; “4+” | 4.0 |

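### The SAP's single high-direction rule for prothrombin time cannot flag impaired clotting in patients whose result is reported as a percentage, a unit the protocol allows

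*SAP*

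**What the plan says.** Protocol section 5.2.3.3 asks for activated partial thromboplastin time (aPTT) or PT, and leaves the PT unit open: "prothrombin time (PT) (expressed either in seconds or as percentage) will be tested". Section 5.2.3 places the safety laboratory work at the sites: "All analyses will be performed locally and the respective reference ranges will be provided in the ISF". The unit can therefore differ from site to site.

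SAP section 7.8.2, Table 7.8.2: 2, lists PT among the secondary tests with one direction of interest and one rule: "Prothrombin Time | High | >ULN and > baseline No CTCAE defined". The row names no unit and has no low-direction rule. For these secondary tests, "analyses will be limited to frequency of patients with potential clinically significant abnormalities". The flag is to be computed on converted values ("liver function categories tables should use converted values" closes the sentence that lists the flag among such analyses). The only percentage conversion the SAP spells out is for another test: "differential blood count is reported in percentage, the following conversion will be applied".

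After the table, the same section also plans counts inside and outside the reference range for tests without CTCAE grading, at baseline, for the maximum on-treatment value and for the last on-treatment value.

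**The concern.** PT in seconds lengthens when clotting is impaired. PT expressed as a percentage of normal activity falls. A rule that looks only upwards is right for the first unit and points the wrong way for the second. The protocol explicitly accepts both, so the SAP row does not fit all the data it may receive.

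What is at stake is the credibility of one line of the safety tables. A row showing no abnormalities could mean that none occurred, or that the rule could not see them. A non-zero count could consist of patients whose clotting was unimpaired. Because the protocol asks for aPTT or PT, a site that chooses PT in percent may have no aPTT result to fall back on.

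**Working it through.** The plan gives no figure to reproduce, so the check is to apply the stated rule to each permitted unit.

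**Rule (SAP Table 7.8.2: 2).** Flag = (value > ULN) and (value > baseline), where ULN and LLN are the upper and lower limits of normal.

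**General argument for percent.** Take impairment in percent as a value below LLN. Since LLN is below ULN, such a value cannot exceed ULN. The first condition fails, so the flag is never raised, whatever the reference range or baseline. Conversely, any percent value that is flagged lies above ULN and so is not a low, impaired value.

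**Illustration.** The reference ranges and values are assumptions; the documents give none.

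| Unit (assumed range) | Baseline → on treatment | Clotting | > ULN? | > baseline? | SAP flag |
|---|---|---|---|---|---|
| Seconds (11–14) | 12 → 22 | impaired | yes | yes | raised, correct |
| Percent (70–130) | 95 → 35 | impaired | no | no | not raised, wrong |
| Percent (70–130) | 110 → 135 | not impaired | yes | yes | raised, wrong |

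**Does another part of SAP 7.8.2 repair this?**

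- *Converted values.* No conversion between percent and seconds is specified for PT. The differential blood count shows that the authors foresaw percentage reporting for one test and wrote a rule for it.
- *Two-sided rows.* The table already carries separate limits where both directions matter, as for phosphate: "High: >1.7 mmol/L and >baseline Low: <0.7 mmol/L and <baseline". PT has only the upper one.
- *Maximum-value reference-range table.* For percent, the maximum is the best value, not the worst. With on-treatment values of 95 and 35 in either order, the maximum is 95, which is in range.
- *Last-value reference-range table.* If the order is 95 then 35, the last value is 35 and is counted as below range. If it is 35 then 95, the last value is 95 and the fall does not appear. The minimum, 35, shows it in both orders.

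**Check of a unit-specific rule for percent.** Flag = (value < LLN) and (value < baseline). For 95 → 35: 35 < 70 and 35 < 95, so flagged. For 110 → 135: 135 is not below 70, so not flagged. Both percent cases are now classified correctly, and the row for seconds is unchanged.

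**The case against.** The strongest reply is that the flag is not the only way a clotting problem could come to light. Protocol sections 5.2.3 and 5.2.6.1.1 have investigators report clinically relevant laboratory changes as adverse events, and these are tabulated. The last-value reference-range table would count a percentage that is still low at the final measurement. This stands. A reader might infer that coagulopathy at percent-reporting sites would go unseen; the documents do not support that. What fails is the flag and the maximum-value table.

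A reader might also infer that the flag is the only planned summary of PT. The SAP is not consistent here. It limits secondary tests to the flag, then describes reference-range tables for tests without CTCAE grading, and PT is marked as having none.

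Third, the row could be read as covering only the time measurement, with percentage results held as a separate test and merely listed. The cited sponsor laboratory standard, which is not available here, might also deal with units. Either is possible, but neither document says so. On the first of these readings percent-reported patients would escape false flags, but they would still have no flag for impairment.

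Finally, a link to the bilirubin increases seen with BI 891065 is tempting. It is indirect: protocol sections 1.2.3 and 4.1.2.1 describe increases of at most Grade 2 and report no clotting signal, and the SAP's potential Hy's law analysis uses ALT, AST and bilirubin, not PT.

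**Conclusion.** The point holds for the clinical-significance flag and for the maximum-value reference-range table. It is a rule with the wrong direction for a permitted unit, not just a missing detail.

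The size cannot be estimated from the documents. If every PT result is in seconds, nothing changes. If every result is in percent, the whole PT row is wrong. The share in percent is not stated and may be zero.

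A reader might take the roughly 12 patients expected in Part A and infer that each misclassified patient moves the frequency by 1/12, or 8.3 percentage points. That is not a valid estimate: SAP section 7 expresses percentages relative to the treatment group, and since the protocol accepts aPTT instead of PT, not every patient need have a PT value.

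The conclusion assumes that percentage results enter this row as reported, and that percent PT falls as clotting worsens. The latter is a general property of the measurement, not something the documents state. PT plays no part in the SAP's analysis of the primary endpoints (the maximum tolerated dose and the number of patients with dose-limiting toxicities), so the consequence is limited to descriptive safety output. A correction is still worth making because it is so cheap.

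**What to change.** In SAP Table 7.8.2: 2, replace the PT row with two:

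- PT in seconds: direction High, above ULN and above baseline.
- PT in percent: direction Low, below LLN and below baseline.

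For percent, use the minimum on-treatment value as the worst value, including in any reference-range table. Do not pool the two units in descriptive statistics. Report one combined count of patients with impaired PT, each classified by the rule for the unit in which the result was reported.

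If all sites report seconds, one sentence in the SAP saying so closes the point. Otherwise the cost is one table row split in two and a few lines of programming, with no new data.

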7.3.5 Safety analyses

Adverse events will be coded using the Medical Dictionary for Drug Regulatory Activities (MedDRA). Standard BI summary tables and listings will be produced. All adverse events with an onset between start of treatment and end of the REP, a period of 30 days after the last dose of trial medication, will be assigned to the on-treatment period for evaluation.

All treated patients will be included in the safety analysis. In general, safety analyses will be descriptive in nature and will be based on BI standards. No hypothesis testing is planned.

Statistical analysis and reporting of adverse events will concentrate on treatment-emergent adverse events, i.e. all adverse events occurring between start of treatment and end of the REP. Adverse events that start before first drug intake and deteriorate under treatment will also be considered as 'treatment-emergent'.

Frequency, severity, and causal relationship of adverse events will be tabulated by system organ class and preferred term after coding according to the current version of the Medical Dictionary for Drug Regulatory Activities (MedDRA) at database lock.

Laboratory data will be analysed both quantitatively as well as qualitatively. The latter will be done via comparison of laboratory data to their reference ranges. Values outside the reference range as well as values defined as clinically relevant will be summarised. Treatment groups will be compared descriptively with regard to distribution parameters as well as with regard to frequency and percentage of patients with abnormal values or clinically relevant abnormal values.

Vital signs, physical examinations, or other safety-relevant data observed at screening, baseline, during the course of the trial and at the end-of-trial evaluation will be assessed with regard to possible changes compared to findings before start of treatment.

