Handling of CTCAE grade -1 and -9 laboratory parameters:

Generally, in case only one direction of worsening (high or low laboratory value) is specified in the CTCAE document, there is no need to examine the other direction. Therefore, for calculating the change in CTCAE grade, patients with a CTCAE grade of -9 (no CTCAE grade defined) will be automatically treated as CTCAE grade 0 for all analyses. In laboratory listings, the CTCAE grade will be displayed as -9.

There are certain parameters for which CTCAE grades can only be attributed by taking physiological consequences into account. These laboratory values will be coded as -1. As these definitions aggregate laboratory data and adverse events or concomitant therapies no analyses based on CTCAE grades will be done. Instead standard laboratory analyses as for laboratory parameters without CTCAE grade definitions will be done. Nevertheless, a laboratory listing including -1 values will be added to the CTR.

Corrected calcium:

The grading of hypocalcemia is based on corrected calcium as calcium can be falsely low if hypoalbuminemia is present. The following corrective calculation will be performed:

$$\text{Corrected calcium (mg/dL)} = \text{Total Calcium (mg/dL)} - 0.8[\text{Albumin (g/dL)} - 4]$$

No correction of the reference range has to be done. The reported reference range of total calcium will be used for analyses.

Corrected calcium can be only derived at a certain time points in case both laboratory values total calcium and albumin have been reported for the patient in the same laboratory sample.

Hepatic enzyme elevations (potential Hy's law cases):

These are defined as those cases where a combination of all of the following events occurred: any on-treatment value of ALT and/or AST $> 3\text{ULN}$ (upper limit of normal) with total bilirubin $\geq 2\text{ULN}$. The events can occur in any order, but must occur within 14 days of the previous event, i.e. the second event must occur within 14 days of the first event, and the third event must occur within 14 days of the second event, etc. Patients with missing laboratory values for liver enzymes will be excluded from these analyses, but presented separately.

Tabulations of hepatic enzyme elevations and liver laboratory values will be done according to the FDA Drug Induced Liver Injury (DILI) guidance ([10](#)).

Hepatic enzyme elevations will be displayed for the treated set for the whole on-treatment period.

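### The SAP 7.8.2 reference-range table for laboratory tests without CTCAE grades uses the maximum and last on-treatment values, so a low value that recovers does not appear in it

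*SAP*

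**What the plan says.** Protocol 7.3.5 makes a general commitment: "Values outside the reference range as well as values defined as clinically relevant will be summarised".

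SAP 7.8.2 carries this out for ungraded tests: "Laboratory values without CTCAE grading will be compared to their reference ranges and frequency tables will be provided". The tables count patients inside and outside that range at baseline, "for the maximum value on treatment and for the last measurement on treatment". The last value is defined by visit: "The last laboratory value on treatment is the laboratory value of the last visit during the on-treatment period of each patient".

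The same handling is extended to parameters coded -1, whose CTCAE grade depends on physiological consequences: "Instead standard laboratory analyses as for laboratory parameters without CTCAE grade definitions will be done".

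For some ungraded tests the SAP treats the low side as of interest. Table 7.8.2: 2 lists chloride and phosphate with both directions, with the low-side rules "Low: <80 mmol/L and <baseline" and "Low: <0.7 mmol/L and <baseline No CTCAE defined".

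Three other statements in SAP 7.8.2 bear on the point:

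- Primary ungraded tests get shift tables by upper and lower reference limits.
- Secondary tests are restricted to clinical-significance frequencies.
- A worst value is calculated for each parameter and is described through its CTCAE grade.

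**The concern.** A table meant to show who left the reference range should register departures in both directions. This one has two on-treatment columns. The first, the maximum, looks upwards only. The second, the last measurement, is a single time point. A fall below the lower limit that corrects itself before the last visit reaches neither column. At stake is a one-sided summary: in this table temporary highs are counted and temporary lows are not, although the Protocol's commitment does not distinguish direction.

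**Working it through.** The analysis is descriptive, so there is no alpha, power or stated figure to reproduce. The check is a matter of definition, confirmed by counting patterns.

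**Inputs.** The columns (baseline, maximum, last) and the definition of the last value come from SAP 7.8.2. The planned size of Part A, about 12 patients, comes from Protocol 3.3 and 7.6. The number of on-treatment values per patient, k, is an assumption, taken from 2 to 5.

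**Step 1: when a low value reaches the table.** The maximum is below the lower limit only if all k values are. The last column is low only if the final value is low. A low value therefore appears only if every value is low or the last one is.

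**Step 2: low and normal values only, last value normal, at least one low.** The number of patterns is 2^(k−1) − 1.

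| k | Patterns | Within range at both maximum and last | Low if the minimum is used |
|---|---|---|---|
| 2 | 1 | 1 | 1 |
| 3 | 3 | 3 | 3 |
| 4 | 7 | 7 | 7 |
| 5 | 15 | 15 | 15 |

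The sequence normal, low, normal is an example. Its maximum and last value are both normal, and only the minimum shows the fall.

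**Step 3: high values also allowed.** Patterns with at least one low value and a last value that is not low number 2 × (3^(k−1) − 2^(k−1)). At k = 5 this is 2 × (81 − 16) = 130. Of these, 15 have no high value and are the patterns of step 2. The other 130 − 15 = 115 have a high maximum, so the patient counts as outside the range on the high side and the low value is still not shown. These are counts of patterns, not probabilities.

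**Step 4: size.** One patient in 12 is 1/12 = 8.3 percentage points. The documents give no rate of temporary low values, so the number of patients affected cannot be estimated.

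**Step 5: could the maximum be loose wording for the worst value?** The SAP describes the worst value separately, in the same section, through the highest CTCAE grade, which ungraded tests do not have. It is not named as an input to this table. The remark that the opposite direction need not be examined applies where CTCAE specifies one direction of worsening, so it does not cover ungraded tests.

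**The case against.** The strongest reply is that the documents may not show any loss.

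- **Chloride and phosphate may not be in the table.** They are secondary tests, which SAP 7.8.2 restricts to clinical-significance frequencies, and those include low-side rules. This stands as an open question: the later sentence on ungraded values has no such restriction, and the two statements are not reconciled.
- **No other affected test can be named.** The other secondary tests marked as having no CTCAE definition (eosinophils, serum protein, prothrombin time) list only the high direction. The rows of the primary-test table are not in the text available here. This also stands, and it limits what can be said about size.
- **Primary tests have other outputs.** Shift tables by upper and lower limits could show low values, and the minimum is among the standard summary statistics in SAP 7. This stands in part. The SAP does not say which on-treatment value feeds the shift tables. If it is the maximum or the last value, the same gap recurs.
- **The sponsor's laboratory standard may specify more.** It is cited but not available here. It may add detail, but the SAP's own sentence is explicit.
- **Clinically relevant abnormalities are reported as adverse events in any case** (Protocol 5.2.3). This is true, and it lowers the stakes.

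A reader might infer that low values go unreported throughout, or that the Protocol's commitment is broken. The outputs just listed do not support either reading. A reader might also infer that the fixed limits for chloride and phosphate are wider than the reference ranges. The documents give no reference ranges (Protocol 5.2.3 leaves them to the local laboratories), so that cannot be shown.

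**Conclusion.** The point holds for this table. As written, a low value that recovers before the last visit is not shown for any ungraded test in the table, nor for the -1 parameters handled the same way. The patient counts as within range, or as high only. This follows from the meaning of a maximum and needs no assumption about the data. Each such patient is about 8 percentage points if 12 are analysed; the number of such patients is unknown.

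The conclusion does not extend to the laboratory analysis as a whole, and it does not depend on chloride and phosphate being in the table. It assumes that the SAP sentence is applied literally and that the sponsor's standard does not override it. The importance is low: the output is descriptive, and the MTD and DLT analyses are unaffected.

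**What to change.** In SAP 7.8.2:

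1. Add the minimum on-treatment value to the reference-range table for ungraded tests, or replace the maximum by the worst value in each direction of interest.
2. State that the shift tables by reference limits use the same on-treatment values.
3. Reconcile the restriction on secondary tests with the sentence covering all ungraded values, so that it is clear whether chloride and phosphate enter the table.

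The cost is one extra column per test and a few sentences of text. No new data are needed.
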